#### 4.0 STATISTICAL METHODS

#### 4.1 Study Hypothesis

A 20% or greater reduction in the proportion of subjects requiring ocular hypotensive medications to reach a target IOP of 19 mmHg or less is a clinically significant treatment effect.

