#### 2.0 STUDY OBJECTIVE AND DESIGN

The objective of this clinical trial is to compare the effectiveness of one *Hydrus* to two iStents for lowering intraocular pressure (IOP) in patients with mild-to-moderate primary open angle glaucoma (POAG), pseudoexfoliative glaucoma (PXG), or pigmentary glaucoma (PG).

This study is a prospective, multicenter, single masked, randomized, clinical trial in which a total of 160 subjects (80 per study arm) will be treated with either one Hydrus or two iStents for treatment of POAG, PXG, or PG in subjects with a phakic lens. The study will be conducted according the Declaration of Helsinki. All study subjects must sign the Informed Consent prior to initiating participation in the study.

Key inclusion criteria for this study are a diagnosis of POAG, PXG, or PG based on optic nerve neuropathy, an open angle, and elevated IOP of 23-39 mmHg in the absence of hypotensive medications. In order to address the confounding effect of medications on the IOP-reducing ability of the devices, a "wash-out" of all glaucoma medications will be conducted, and a 'diurnal' methodology will be utilized to determine the subject's eligibility. The duration of wash-out will be determined by the specific medication(s) used.

Upon successfully meeting the study inclusion/exclusion criteria, subjects will be scheduled for surgery. Randomization will take place on the day of surgery just prior to treatment. Randomization sequence will be based on pre-determined computer-generated lists.

Follow up will be continued for 2 years post-surgery, and will include assessments of the subject's IOP, ocular health, and visual acuity status. Visits will be conducted at 1, 7, 30, 180, 365, 540, and 730 days.

In the event a study subject does not respond to device therapy, hypotensive glaucoma medications may be prescribed in order to reduce IOP to a safe level, as determined by the judgment of the attending physician. Medications of the same type used prior to wash out will be re-started in this event. Re-medication will not be considered an adverse event, but will be monitored. Neither the Hydrus nor the iStent devices preclude the ability to later perform filtration surgery, in the event medications do not lower pressure adequately and more invasive therapy is required.

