#### 3.0 STUDY ENDPOINTS

The primary effectiveness endpoint for this study is the proportion subjects with IOP ≤19 mmHg *and* without the use of ocular hypotensive medications at 12 months, as measured by Goldmann tonometry.

Secondary effectiveness endpoints include:

- The proportion of subjects who are are not using ocular hypotensive medications at 12 and 24 months, as measured by Goldmann tonometry
- Mean medication use at 12 and 24 months
- The proportion subjects with IOP ≤19 mmHg *and* without the use of ocular hypotensive medications at 24 months, as measured by Goldmann tonometry

Safety endpoints include:

- Frequency of loss in BCVA of 2 lines or more at 12 and 24 months,
- Slit lamp and fundus examination findings at 12 and 24 months,
- Frequency of complications and adverse events at all follow up periods.

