# 4.2 Sample Size

The study size is based on the primary endpoint.

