# 4.3 Safety Analysis

Safety data (adverse events, visual acuity measurements, perimetry, and ocular health findings based on slit lamp and fundus examinations) will be evaluated using descriptive

statistics. Frequency tabulations of safety outcomes will be performed for 1, 3, 6, 12, 18 and 24-month follow up periods. Safety analysis cohorts will be grouped by actual treatment. The study is not designed to detect differences in safety outcomes.

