### **6.3** Goldmann Tonometry Procedure

At the baseline, IOP will be assessed using diurnal Goldmann tonometry, after wash-out of hypotensive medications. In this study, 3 IOP readings will be taken during daylight hours as follows:

o Time 1: 9:00 AM (± 1 hour)

- $\circ$  Time 2: 4 hours later ( $\pm$  1 hour) than Time 1
- o Time 3: 4 hours later ( $\pm$  1 hour) than Time 2

A minimum of 2 IOP readings are to be taken at each time point. If the first two IOP values at a time point are more than 2 mm apart, then a third reading should be taken.

To calculate the mean diurnal IOP, the mean IOP value from each time point is used to calculate a grand average. In the event one or more of the time points requires a third IOP reading, then the median IOP of that time point is used for the calculation of the mean diurnal IOP.

IOP readings taken at screening and at all other follow up visits will be taken once during the visit at 9 AM  $\pm$  2 hours. A minimum of 2 IOP readings are to be taken. The mean of these readings will be used for the IOP value at that visit. If the first two IOP readings are more than 2 mm apart, then a third reading should be taken. In this case the median of the 3 values will be used as the value for the visit.

If the subject meets all criteria at the Baseline visit, he or she will be scheduled for surgery within 21 days of this visit. On the day of surgery, the subject will be randomized to either the Hydrus group or iStent group. Computer-generated randomization lists will be used, with separate randomization lists for each clinical site. The subject will not be informed of the randomization assignment and all study personnel will be instructed to maintain the "masking" of the treatment assignments.

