# 6.9 Subject Disposition

Subjects may be terminated (exited) from the study early due to:

- Screening failure,
- A threat to the subject's health emerges in the course of following study procedures,
- Inability to continue with the study, and
- Voluntary withdrawal.

Subjects who are terminated due to screening failure will not be followed beyond the date of screening failure. For safety reasons, randomized subjects who are terminated should receive routine clinical follow up until the planned end of the study period. CRF's will not be completed for terminated subjects. Terminated subjects will not be replaced. Notification of a subject's early termination should be made immediately to the sponsor and documented on the appropriate CRF.

Completed subjects are those subjects who have not been terminated from the study prior to completion of follow up.

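### Section 4 names no primary effectiveness analysis, Section 4.1's 20% has no stated scale and does not clearly match the endpoint, and Section 6.9 leaves 12-month outcomes unrecorded

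*Combined protocol and SAP*

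**What the plan says.** - **Endpoint (Section 3.0).** The primary endpoint is the proportion with IOP at or below 19 mmHg and "without the use of ocular hypotensive medications at 12 months, as measured by Goldmann tonometry".
- **Threshold (Section 4.1).** One sentence calls "A 20% or greater reduction in the proportion of subjects requiring ocular hypotensive medications to reach a target IOP of 19 mmHg or less" clinically significant. It gives no scale, comparator or time point.
- **Size (Sections 2.0 and 4.2).** Section 2.0 states that "a total of 160 subjects (80 per study arm) will be treated with either one Hydrus or two iStents". Section 4.2 consists of "The study size is based on the primary endpoint".
- **Analysis (Section 4.3).** The only methods given are descriptive and for safety. The only analysis set is also for safety: "Safety analysis cohorts will be grouped by actual treatment". The table of contents lists nothing beyond 4.1 to 4.3 under statistical methods, and these sections carry no redaction mark.
- **Randomisation and baseline (Sections 5.1 and 6.3).** Lists are computer-generated, "with separate randomization lists for each clinical site". Mean diurnal IOP after wash-out is measured at baseline in every subject and must lie within 23-39 mmHg.
- **Early exit (Section 6.9).** For safety, "randomized subjects who are terminated should receive routine clinical follow up until the planned end of the study period", yet case report forms "will not be completed for terminated subjects. Terminated subjects will not be replaced".

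**The concern.** Three choices that can change the reported result are left open.

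1. **The primary comparison.** Without a test, significance level, analysis set or missing-outcome rule, each can be chosen once the data are known. Grouping by actual treatment is laid down for safety, and nothing says that effectiveness follows the assigned arm. Site and baseline IOP have no role in an effectiveness analysis.
2. **The meaning of 20%.** It is the plan's only effect threshold. If it is used to interpret the result, the more favourable scale can be picked afterwards. Its quantity, subjects who need medication to reach target, also differs in wording from the endpoint.
3. **Outcomes after termination.** Section 6.9 keeps terminated randomised subjects in clinical care but stops their study records. Their 12-month IOP and medication status may exist and still not be captured. If losses differ between arms, the comparison can be biased.

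**Working it through.** **Inputs.** From the documents: 80 per arm, the 20% and the Section 3.0 endpoint. Assumed, because the plan gives none: two-sided 5%, 80% power, iStent failure rates of 30% to 90%, complete data unless stated. Failure means not meeting the Section 3.0 endpoint.

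**1. Do 4.1 and 3.0 describe the same quantity?** Take an unmedicated subject at 12 months with IOP above 19 mmHg. Under 3.0 this is a failure. Under 4.1 the subject is not on medication, and whether medication is required is a judgement. The two are not clearly complements.

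**2. Does the 160 settle the scale?** It cannot be reproduced from the plan's own inputs, so assumed ones were tried:

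n per arm = [1.96·√(2p̄(1−p̄)) + 0.842·√(p₁(1−p₁)+p₂(1−p₂))]² / (p₁−p₂)²

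For 80% versus 60% failure: (1.96×0.648 + 0.842×0.632)² / 0.04 = 3.25/0.04, about 81.2, so 82. Eighty per arm fits an absolute 20 points at iStent failure of about 38-40% or 80-82%, and a relative 20% at about 89%. Power at 80 per arm:

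| iStent failure | 90% | 80% | 70% | 60% | 50% | 40% | 30% |
|---|---|---|---|---|---|---|---|
| absolute 20 points | 89% | 79% | 74% | 72% | 74% | 79% | 89% |
| relative 20% | 83% | 62% | 45% | 33% | 24% | 18% | 13% |

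The size fits the absolute reading over more control rates, but does not decide it.

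**3. What does the scale change?** Take failures of 60/80 (iStent) and 47/80 (Hydrus).
- Difference 13/80 = 16.3 points; Wald 95% CI 0.1625 ± 1.96×0.0733 = 1.9 to 30.6 points.
- Relative reduction 13/60 = 21.7%.
- Pooled z = 0.1625/0.0744 = 2.18, p = 0.029 (Fisher 0.043).

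The result is below 20 on one scale and above it on the other. On success instead of failure, the change is 20/80 to 33/80, a 65% relative rise, so a relative threshold must name failure.

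Enumerating all tables with 80 per arm (pooled z test): a significant Hydrus benefit never needs more than 13 fewer failures, whereas 20 points needs 16. Up to 60/80 iStent failures, every significant benefit is already at least 20% relative. No significant result meets the absolute reading and misses the relative one. At a true 15 to 20 points, the chance of a significant result that the two scales label differently is 18% to 22% for iStent failure of 50% to 80% (25% to 42% of significant results). It is 7% to 10% at 90% failure and 36% to 39% at 30%.

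**4. What can a missing-outcome rule do?** Assume success of 40% (iStent) and 60% (Hydrus), and loss unrelated to outcome. Counting missing as failure gives:
- 10% lost in each arm: 0.6×0.90 − 0.4×0.90 = 18 points.
- 5% iStent, 15% Hydrus: 0.6×0.85 − 0.4×0.95 = 13 points.
- 15% iStent, 5% Hydrus: 0.6×0.95 − 0.4×0.85 = 23 points.

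**5. What does adjustment cost?** A simulation (8,000 trials per setting) assumed success of 40% versus 60%, 10 sites of 16 or 5 of 32, and baseline IOP normal (26.5, SD 3.5) truncated to 23-39. With leverage-corrected robust errors, power moved from 73% to 71.5% (10 sites) and from 72.2% to 71.6% (5 sites) when neither covariate was prognostic. It rose by 2 to 4 points with moderate and 5 to 6 with stronger effects. Null rejection was 4.3% to 4.6%, against 5.5% to 6.6% with model-based errors.

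**The case against.** The strongest reply is that 4.1 sets no rule. It says what size of effect is clinically significant, and could simply be the planning difference behind 4.2. A reader might infer that the observed estimate must reach 20% for the trial to succeed. The documents do not say so, and the disagreement probabilities above matter only if the 20% is used to interpret the observed result. Making it a hurdle would also be costly: with 80 per arm and a true 20 points, an observed difference of 20 points or more occurs only about 54% of the time, while the test is significant 72% to 80% of the time at iStent failure of 50% to 80%. This objection stands, and no such hurdle is proposed.

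It is also fair that comparator, time point and endpoint can be inferred from Sections 2.0, 3.0 and 4.2, and that the p-value for equal proportions is the same on either scale. The power table leans towards the absolute reading. Site and baseline IOP do have other roles: site defines the randomisation lists, and baseline IOP decides eligibility and anchors the IOP-spike definition in Section 7.3. What they lack is a role in an effectiveness analysis.

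Finally, the adjusted model is one defensible choice among several, its simulation rests on site numbers and a baseline distribution that the documents do not give, and routine-care IOP may not follow Section 6.3. None of this supplies the missing analysis or recovers outcomes after termination.

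**Conclusion.** The point holds. The plan has no primary effectiveness analysis, its one effect threshold has no scale and is not clearly aligned with the endpoint, and Section 6.9 discards 12-month outcomes that may be available. The gaps in analysis and data capture come first; the scale comes second.

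The size depends on assumptions. With 40% versus 60% success and 5% to 15% loss, a missing-as-failure rule gives anything from 13 to 23 points for a true 20. The scale would change the label, but not the p-value, of roughly a fifth of trials at a true 15 to 20 points with iStent failure of 50% to 80%, and only if the 20% is used as a benchmark.

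A reader might also infer that 160 subjects is the wrong number. The documents do not support that: it cannot be verified from the plan, but it fits several plausible sets of inputs.

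**What to change.** Before any comparative 12-month data are examined:

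1. **Add a primary analysis to Section 4.** Analyse all randomised subjects by assigned arm on the Section 3.0 endpoint at 12 months, two-sided 5%. Use logistic regression on arm, site (small sites pooled) and baseline mean diurnal IOP. Report the standardised risk difference with a 95% CI from leverage-corrected robust or bootstrap errors. Cost: one new section and its programming, and about 1 point of power if neither covariate is prognostic.
2. **Change Section 6.9.** Record 12-month IOP and medication status of terminated randomised subjects from routine care where consent allows, and flag IOP not taken by the Section 6.3 procedure. Impute what is still missing within arm from baseline IOP and the last recorded IOP and medication status. Count missing as failure in a sensitivity analysis. Cost: one record look-up per terminated subject.
3. **Restate 4.1** on failure of the Section 3.0 endpoint (IOP above 19 mmHg or on medication), Hydrus versus two iStents. The sponsor declares the 20% as absolute points or as a relative reduction in failure (risk ratio of failure, from the same model). The sponsor also says whether it is a planning difference or a benchmark for interpretation, with no pass mark on the point estimate. Cost: rewording, and commitment to one scale.

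No new subjects, study visits or measurements are needed, and no enlargement is asked for.

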# 4.2 Sample Size

The study size is based on the primary endpoint.

# 4.3 Safety Analysis

Safety data (adverse events, visual acuity measurements, perimetry, and ocular health findings based on slit lamp and fundus examinations) will be evaluated using descriptive

statistics. Frequency tabulations of safety outcomes will be performed for 1, 3, 6, 12, 18 and 24-month follow up periods. Safety analysis cohorts will be grouped by actual treatment. The study is not designed to detect differences in safety outcomes.

#### 5.0 STUDY POPULATION

#### 5.1 Inclusion Criteria

Subjects who meet the following inclusion and exclusion criteria will be eligible for enrollment in this study. Ocular criteria relates to the study eye only.

- Male and female patients from 45 to 84 years of age.
- A diagnosis of primary open angle glaucoma (POAG), pseudoexfoliative glaucoma (PXG), or pigmentary glaucoma (PG).
- A phakic patient with BCVA of 20/30 or better.
- A pseudophakic patient who has had cataract surgery >6 months from the time of study enrollment.
- Subject is on  $\geq 2$  glaucoma medications at Screening.
- Normal angle anatomy by gonioscopy with a Shaffer angle grade of ≥III in all four quadrants.
- Optic nerve pathology characteristic of glaucoma described by at least one of the following:
  - A) Thinning, narrowing, or notching of the optic disc rim.
  - B) Diffuse optic disc cupping or asymmetric cupping.
  - C) Diffuse or localized peripapillary retinal nerve fiber layer loss.
- After glaucoma medication wash-out, a mean diurnal IOP of 23-39 mmHg by Goldmann applanation tonometry.
- The subject can safely tolerate periodic wash out of glaucoma medications.
- The subject is able to understand the requirements of the study and is willing to follow study instructions, provide written informed consent, and agree to comply with all study requirements.

#### **5.2** Exclusion Criteria

Excluded from the study will be individuals with the following characteristics. Unless specified otherwise, all ocular criteria refer to the study eye only.

- Other secondary glaucoma (such as neovascular, uveitic, traumatic, steroid induced, lens induced, or glaucoma associated with increased episcleral venous pressure).
- Closed angle forms of glaucoma.
- Diagnosis of acute angle closure, congenital, malignant, or developmental glaucoma.

- Use of <2 or >4 ocular hypotensive medications. (Note: Combination medications count as 2 medications.)
- Use of oral hypotensive medication(s) for glaucoma treatment of the fellow eye.
- Previous incisional glaucoma surgery of any kind, including non-penetrating procedures such as deep sclerectomy or canaloplasty.
- Significant ocular health risk by washout of medication.
- Central corneal thickness >620 or <480 microns.
- Proliferative diabetic retinopathy.
- Previous surgery for retinal detachment.
- Clinically significant corneal dystrophy.
- Previous corneal surgery.
- Previous refractive surgery.
- Degenerative visual disorders such as wet age-related macular degeneration.
- Clinically significant ocular pathology, other than glaucoma.
- Clinically significant ocular inflammation or infection within thirty days prior to screening.
- Uncontrolled systemic disease that in the opinion of the Investigator would put the subject's health at risk and/or prevent the subject from completing all study visits.
- Pregnant, nursing females or women of child-bearing potential who are not using an acceptable method of contraception.

#### 6.0 STUDY PROCEDURES

### 6.1 Subject Entry, Consent and Enrollment

Participants will be recruited from the Investigators' patient population or referrals. Patients that appear to be eligible will be approached for study participation and sign a patient informed consent (PIC) prior to the commencement of study related procedures.

The investigator or designee will explain the study purpose, procedures, and subject responsibilities to the potential participant. The subject should be given the opportunity to ask questions and allowed time to consider the information provided. The subject's willingness and ability to meet the follow-up requirements will be determined. When it has been established that the subject is eligible for possible enrollment into the study, written informed consent will be obtained. One copy of the informed consent form will be retained with the subject's medical records, and one copy will be provided to the subject.

Only one qualified eye per qualified subject may be randomized for treatment. If both eyes qualify for enrollment, the eye with the worse best corrected visual acuity will be designated as the study eye.

#### **6.2** Medication Wash Out

After the subject has successfully completed the preoperative screening exam, he or she will be instructed to discontinue any ocular hypotensive medications in the designated treatment eye for the appropriate washout period, as listed in Table 1, *prior to* the Baseline Exam. If upon washout, the subject experiences an IOP elevation to greater than 39 mmHg, or requires the reintroduction of hypotensive medications or a surgical intervention during the preoperative period, the subject will be treated appropriately and excluded from the study. Any subject whose IOP does not fall within 23-39 mmHg will be exited from the study.

TABLE 1 OCULAR HYPOTENSIVE MEDICATION WASHOUT PERIODS									
Carbonic Anhydrase Inhibitors									
Diamox® (Acetazolamide) – oral Rx	14 days								
Neptazane® (Methazolamide) – oral Rx	14 days								
Azopt® (Brinzolamide)	14 days								
Trusopt® (Dorzolamide Hydrochloride)	14 days								
Alpha Adrenergic Agonist									
Alphagan® (Brimonidine)	14 days								
Iopidine® (Apraclonidine Hydrochloride)	14 days								
Beta Blockers									
Betagan® (Levobunolol Hydrochloride)	28 days								
Betoptic® (Betaxalol Hydrochloride)	28 days								
OptiPranolol® (Metipranolol)	28 days								
Timoptic/Betimol® (Timolol Maleate)	28 days								
Prostaglandin Analogs									
Lumigan® (Bimatoprost)	28 days								
Travatan® (Travoprost)	28 days								
Xalatan® (Latanoprost)	28 days								
Combined Medications									
Combigan® (Brimonidine Tartrate/Timolol Maleate)	28 days								
Cosopt® (Dorzolamide Hydrochloride/ Timolol Maleate)	28 days								

### **6.3** Goldmann Tonometry Procedure

At the baseline, IOP will be assessed using diurnal Goldmann tonometry, after wash-out of hypotensive medications. In this study, 3 IOP readings will be taken during daylight hours as follows:

o Time 1: 9:00 AM (± 1 hour)

- $\circ$  Time 2: 4 hours later ( $\pm$  1 hour) than Time 1
- o Time 3: 4 hours later ( $\pm$  1 hour) than Time 2

A minimum of 2 IOP readings are to be taken at each time point. If the first two IOP values at a time point are more than 2 mm apart, then a third reading should be taken.

To calculate the mean diurnal IOP, the mean IOP value from each time point is used to calculate a grand average. In the event one or more of the time points requires a third IOP reading, then the median IOP of that time point is used for the calculation of the mean diurnal IOP.

IOP readings taken at screening and at all other follow up visits will be taken once during the visit at 9 AM  $\pm$  2 hours. A minimum of 2 IOP readings are to be taken. The mean of these readings will be used for the IOP value at that visit. If the first two IOP readings are more than 2 mm apart, then a third reading should be taken. In this case the median of the 3 values will be used as the value for the visit.

If the subject meets all criteria at the Baseline visit, he or she will be scheduled for surgery within 21 days of this visit. On the day of surgery, the subject will be randomized to either the Hydrus group or iStent group. Computer-generated randomization lists will be used, with separate randomization lists for each clinical site. The subject will not be informed of the randomization assignment and all study personnel will be instructed to maintain the "masking" of the treatment assignments.

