### 6.8 Postoperative Ocular Hypotensive Medications

Since the implantation procedure involves the use of an ophthalmic viscoelastic agent and post-operative steroids, both of which are known to cause IOP elevation in some cases, use of glaucoma medications in the first month after surgery is expected. The first line hypotensive medication in the immediate post-operative period (0-60 days) should be selected from the beta blocker class (if tolerated) as indicated in the table below. In these cases, additional visits may be performed to assess IOP, and medications discontinued if the patient's IOP allows.

Long term medical therapy (defined as medications prescribed at or after the 90-day visit) may be implemented at the Investigator's discretion in order to maintain a safe IOP.

Patient medication usage (medication class, dose, frequency, and brand, if applicable) will be collected at the time of screening. The medications should be assigned a rank order for the purpose of potential reintroduction. If post-operative IOP increases to an unsafe level, ocular hypotensive medications should be reintroduced one at a time and following the order indicated at screening.

If a medication prescribed in the immediate post-operative period does not match the class indicated on the screening list and is continued to the 3 month visit, then the subject should be switched to the pre-surgical medication class and dose if possible.

Reintroduction of ocular hypotensive medication will be recorded in the appropriate Case Report Form, along with the clinical rationale for the decision to apply medications. A record of all medications added, discontinued or changed will be documented on the appropriate Case Report Form.

Because the use of ocular hypotensive medications to control IOP is a study endpoint, the CRF describing the introduction or discontinuation will be reviewed by the Medical Monitor for appropriateness and consistency across study groups. The Medical Monitor will be masked to the identity of the treatment subject.

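### Randomisation is by site, but no effectiveness test is named and site enters no analysis; an unstratified comparison would be conservative if the lists are balanced within site and site is prognostic

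*Combined protocol and SAP*

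**What the plan says.** Section 2.0 describes a multicentre randomised trial in which "a total of 160 subjects (80 per study arm) will be treated with either one Hydrus or two iStents". On the sequence it adds only this: "Randomization sequence will be based on pre-determined computer-generated lists". Section 6.3 is more specific: "Computer-generated randomization lists will be used, with separate randomization lists for each clinical site". Neither section says whether the lists are blocked, and the number of sites is not given.

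The primary endpoint in Section 3.0 is binary: IOP of 19 mmHg or less and no hypotensive medication at 12 months. The secondary endpoints are the same composite at 24 months, the medication-free proportion at 12 and 24 months, and mean medication use at 12 and 24 months.

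Section 4 has three parts. Section 4.1 states an effect regarded as clinically significant: "A 20% or greater reduction in the proportion of subjects requiring ocular hypotensive medications to reach a target IOP of 19 mmHg or less". Section 4.2 reads in full: "The study size is based on the primary endpoint." Section 4.3 covers safety and is descriptive. No effectiveness test, model, interval, alpha or covariate is named anywhere.

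Section 6.8 lets long-term medication be started at the investigator's "discretion in order to maintain a safe IOP", without an IOP threshold. It also has a masked Medical Monitor review medication changes for consistency across study groups.

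**The concern.** When allocation is fixed within a stratum and the stratum predicts outcome, the treatment difference varies less from trial to trial than an unstratified standard error assumes. The interval is then too wide, the test rejects too rarely under the null, and some power is lost.

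Site could well predict outcome here. Half of the success definition is freedom from medication, and the decision to prescribe rests partly with each investigator. A site that prescribes readily would have fewer successes in both arms. The same discretion drives the medication-free proportion and mean medication use.

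As Section 4 stands, a plain two-proportion test is open to the sponsor. So is a decision, taken after the data are seen, on whether to adjust for site. With 80 per arm, a few points of power can matter.

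**Working it through.** **1. The plan's own figure.** The total of 160 cannot be reproduced, because alpha, sidedness, power and the control rate are not stated, nor whether the 20% is absolute or relative. I take it as 20 points absolute, with a two-sided 5% test. The usual formula is

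n per arm = [1.96·√(2p̄(1−p̄)) + 0.842·√(p₁(1−p₁)+p₂(1−p₂))]² / (p₁−p₂)².

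- 20% vs 40%: (1.270 + 0.532)²/0.04 = 81.2, so 82 per arm. Power at 80 per arm is 79.4%.
- 40% vs 60%: (1.386 + 0.583)²/0.04 = 96.9, so 97 per arm. Power at 80 per arm is Φ[(0.20 − 1.96×0.0791)/0.0775] = Φ(0.58) = 72%.

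Across control rates, 80% power needs 62 to 97 per arm, and 80 per arm gives 72% to 89% power. Nothing in the plan identifies the choice made.

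**2. Inputs for the site question.** From the documents: 160 subjects, 1:1, separate list per site, binary primary endpoint. Assumed: 8, 10 or 16 equal sites; two-sided 5%; 40% vs 60% success; no dropout; logit-normal site effects. Spread of true site rates around 40%, from logit(0.40) = −0.405:

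- SD 0.5: −0.405 ± 0.98, so 95% of sites lie between about 20% and 64%.
- SD 1.0: −0.405 ± 1.96, so 95% of sites lie between about 9% and 83%.

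**3. Simulation at 40% vs 60%.** The unstratified pooled z-test is compared with the site-stratified Cochran-Mantel-Haenszel (CMH) test.

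| Lists | Site SD | Result |
|---|---|---|
| Balanced within site | 0 | No power difference |
| Balanced within site | 0.5 | Stratified about 2 points higher |
| Balanced within site | 1.0 | 73% unstratified, 79% stratified; unstratified type I error 3.1–3.5% |
| Unblocked | 0 (16 sites) | Stratified about 4 points lower |
| Unblocked | 0.5 (10 sites) | 71.8% with either test |
| Unblocked | 1.0 | Stratified 3–5 points higher (10 sites: 72.8% vs 77.1%) |

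For 10 balanced sites at SD 1.0, the mean standard error is 0.0763 unstratified and 0.0705 stratified. The ratio is 1.082, and 1.082² = 1.17, equivalent to about 17% more subjects. If the true spread is the smaller figure, the expected type I error is 2[1 − Φ(1.96 × 1.082)] = 3.4%, which agrees with the simulated range.

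**4. Sensitivity to the assumed rates.** The same comparison at 30% vs 50%, 10 sites, 20,000 trials per cell, permuted blocks of 4 where blocked. Each power cell is unstratified / stratified. The SE ratio is the unstratified SE over the true SD under the null.

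| Site SD | Blocked: power | Type I, unstratified | SE ratio | Unblocked: power | Type I, unstratified |
|---|---|---|---|---|---|
| 0 | 73.0% / 73.4% | 4.9% | 1.00 | 73.9% / 71.2% | 5.1% |
| 0.5 | 74.0% / 76.0% | 4.6% | 1.02 | 73.9% / 73.2% | 5.2% |
| 1.0 | 76.0% / 81.6% | 3.5% | 1.07 | 74.2% / 78.3% | 5.3% |
| 1.5 | 76.4% / 86.1% | 2.4% | 1.15 | 74.1% / 83.5% | 5.3% |

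With 16 unblocked sites and no site effect, the figures are 74.1% and 69.4%, a loss of 4.7 points from stratifying. The pattern matches step 3.

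**The case against.** The strongest reply is that the plan does not choose an unstratified analysis; it names no effectiveness analysis at all. This stands. A reader might infer from Section 4 that the sponsor intends to ignore site, but the documents do not support that. The larger gap is the missing primary method, and the handling of site is one part of it.

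A reader might also infer that the intervals will be too wide. That needs balance within site and a prognostic site effect, and neither is stated. The planned 80 per arm hints at balanced lists, since simple 1:1 allocation of 160 gives exactly 80/80 with probability of about √(2/(160π)) = 6%. But 80 may be only a target. With unblocked lists the unstratified error rate stays near 5%, and stratifying over many small sites can cost power.

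The 6-point figure rests on SD 1.0, a wide spread of site rates that nothing in the documents supports. Section 6.8 also limits prescribing differences, through the screening rank order for reintroduction and the Medical Monitor's review. That review is described as across study groups, not across sites, so it weakens the case for a site effect without removing it.

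Finally, any error with balanced lists is on the conservative side, so the validity of a positive result is not threatened.

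**Conclusion.** The point holds in conditional form. It is certain that randomisation is by site, that no effectiveness test is named, and that site enters no analysis. The consequence depends on three things the documents leave open: whether the comparison is unstratified, whether lists are balanced within site, and how strongly site predicts outcome.

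If all three apply, the standard error is too large. At 40% vs 60% with 8 to 16 sites, the loss is about 2 power points at SD 0.5 and about 6 at SD 1.0; it is about 0 if site has no effect. If lists are unblocked, the unstratified test is sound, and stratifying ranges from a 3 to 5 point gain (SD 1.0) to a loss of about 4 (16 small sites, no site effect). Site numbers, rates, alpha and site SDs are all assumptions.

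The change is worth making because it is nearly free and also supplies a primary method where none is given. Confidence is high in the omission and moderate in the size of the loss.

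**What to change.** Add to Section 4:

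- The primary endpoint and the binary secondary endpoints are compared by a site-stratified Mantel-Haenszel risk difference with 95% CI, tested with the Cochran-Mantel-Haenszel test.
- Mean medication use is analysed in a model with treatment and site.
- Very small sites, and sites with subjects in only one arm, are pooled by a stated rule fixed before unmasking. The sponsor should set the size threshold once site numbers are known.

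Add to Section 2.0 or 6.3 whether the lists are blocked within site. Block sizes can stay in a restricted document.

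Lens status should not be added as a further stratum on this argument, because the trial does not randomise by it, and crossing it with site would make the strata smaller still.

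The cost is a few lines of text and the pooling rule, with no new data. The one statistical downside is a possible slight loss of power if the lists are unblocked and the sites are many and small, which the pooling rule is meant to limit.
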